A Third-Wave Intervention for Internalized Weight Bias Combined With a Weight Loss
Program Using Video Conferencing Software

NCT Number: Not yet assigned

Document Date: 08/11/2022

Study Protocol & Statistical Analysis

Participants

Participants will be recruited for the study using an email Listerv announcement to individuals throughout the university and associated community. Participants must indicate that they are interested in weight loss and are interested in participation for the entire program before being accepted. Other inclusion and exclusion criteria require that participants be 18 or older, at a BMI of 25 kg/m² or greater, and are not pregnant or planning to become pregnant. Based on average scores for Durso and Latner's (2008) Weight Bias Internalization Scale and in staying consistent with Pearl, Wadden, Bach, Gruber, et al.'s (2020) research, individuals will also be screened for higher-than-average levels of IWBI, with a cutoff of 4 or higher. Individuals who have already successfully lost more than 5% of their body weight within the past six months will be excluded. Individuals with current use of medication prescribed for weight loss (such as orlistat, sibutramine, or rimonabant) will also be excluded. In addition, participants must have access to internet, along with a web camera and sound, and be able to use video conferencing software and attend weekly online groups. They will also need access to a reliable scale to weigh themselves weekly.

According to an a priori analyses run using G*Power, a sample size of 40 will be required to detect a medium effect size for a 2 x 2 repeated measures analysis of variance (ANOVA; Faul et al., 2007). A medium effect size was selected for a couple of reasons. First, this is consistent with previous literature, as Pearl, Wadden, Bach, Gruber, et al. (2020) also structured their methodology on detecting a medium effect size. Second, this study aims to examine the efficacy of an intervention. However, an intervention that produces only a small effect may be

less clinically meaningful than an intervention that produces a medium or large effect size. Due to attrition concerns, the sample size for the proposed study will be 70, with 35 individuals per group.

Interventions

Diabetes Prevention Program (DPP). All participants will participate in a behavioral weight loss program (BWLP). The program will be a 12-week adapted version of the DPP. As previously mentioned, the DPP is a widely used, evidence-based program that has been found to be applicable to individuals of varied backgrounds, and has overall become the gold-standard for behavioral weight loss programs (DPP Research Group, 2002a). Several studies have found the DPP to produce statistically significant weight loss when delivered through an online format (Azar et al., 2015; Carels et al., 2021; Vadheim et al., 2010). See Appendix A for a list of session topics.

Third-Wave Based Internalized Weight Bias Intervention. ACT-based programs and self-compassion have shown promise throughout research for lowering IWB (Berman et al., 2016; Levin et al., 2018; Lillis et al., 2009; Palmeira, Cunha, & Pinto-Gouveia, 2017; Palmeira, Pinto-Gouveia, & Cunha, 2017; Forbes et al., 2020). Therefore, using techniques from prior ACT- and self-compassion based programs, a weight bias reduction intervention will be administered. Session topics will include psychoeducation, observing myths and stereotypes, and using internal and external coping for weight bias, and these topics will be viewed through a self-compassionate and ACT-based or DBT-based lens (for example, participants may defuse from internal critical thoughts rather than challenge them). Sessions will also cover acceptance, cognitive defusion, mindfulness, committed action, and self-compassion. Participants will be

asked to keep a self-compassion journal to practice third-wave and self-compassion skills and techniques. See Appendix B for a list of session topics.

Procedure

Participants will complete an initial digital screener to determine eligibility. Once it is determined that eligibility criteria are met, participants will be randomly assigned into one of two groups. Both groups will initially receive a weight loss intervention using the DPP through twelve weekly, hour long virtual sessions as led by clinical health psychology doctoral students with previous weight loss intervention experience. In addition, group leaders will look for opportunities to incorporate weight bias reduction strategies throughout the DPP when possible. However, only one group will be administered a third-wave, ACT and self-compassion-based IWB intervention for 30 minutes after the 60 minute weight loss intervention. Both groups will receive information on how to monitor eating behavior through MyFitnessPal, exercise through MyFitnessPal or smart devices, and will be encouraged to weigh themselves weekly or more. The IWB program will begin after the first four sessions of the DPP so that participants can spend the first month adjusting to weight loss treatment.

Measures

All measures will be completed at baseline and post-intervention online. Demographic information will also be collected at baseline. In addition, participant weight and height will be collected in person, using a digital scale and stadiometer, at baseline and post-intervention. If participants drop out of the study, they will be asked to complete the post-intervention surveys and attend a weigh-in, if possible.

Demographics. All participants will complete demographic questions assessing age, sex, gender, race/ethnicity, sexual orientation, income, education, and self-reported height and weight. Participants will also be asked about their desire for weight loss.

Internalized Weight Bias. IWB will be measured by both the Weight Bias Internalization Scale (WBIS; Durso & Latner, 2008; Appendix C) and Weight Self-Stigma Questionnaire (WSSQ; Lillis et al., 2010; Appendix D). Both measures were chosen for several reasons. First, Pearl, Wadden, Bach, Gruber, et al. (2020) found participant differences on the WSSQ at a 12-week assessment of IWB, but did not see a change on the WBIS. Second, while both are commonly used throughout IWB literature, some IWB interventions only used the WSSQ (Lillis et al., 2009; Palmeira, Cunha, & Pinto-Gouveia, 2017) and some only used the WBIS (Pearl, Hopkins, et al., 2018). Because this study aims to build upon previous approaches to lowering IWB, both scales will be considered to increase generalizability to all relevant past findings. Both scales have been found to be predictive of IWB, have comparable reliability convergent validity, and are strongly correlated (Hübner et al., 2016).

In 2008, Durso and Latner developed the WBIS, which was an 11-item scale used to assess IWB among populations with overweight and obesity using a 7-point Likert scale. According to the authors, the scale was created using existing literature on antifat attitudes and similar questionnaires on internalized homophobia. The WBIS uses questions that assess the extent to which an individual accepts or rejects their weight (e.g., “Because I’m overweight, I don’t feel like my true self.”), the desire to change their weight (e.g., “I wish I could drastically change my weight.”), or how their weight influences their self-perception or mood (“I am less attractive than most other people because of my weight.”). The authors report excellent

internal consistency ($\alpha = 0.90$) for the scale. In addition, they reported good validity as the WBIS was moderately correlated with measures of antifat attitudes, self-esteem, and body image concerns when controlling for BMI.

Another scale developed by Lillis et al. (2010), entitled the Weight Self-Stigma Questionnaire (WSSQ), uses 12 items to assess IWB among populations with overweight status and obesity on a 5-point Likert scale. The study has two factors; the self-devaluation subscale (with items such as “I feel guilty because of my weight problems” and “I caused my weight problems”) and the fear of enacted stigma subscale (with items such as “People discriminate against me because I’ve had weight problems” and “Others will think I lack self-control because of my weight problems”). The scale was developed based on substance abuse stigma. The WSSQ was found to have good internal consistency ($\alpha = 0.88$) overall, as well as for the subscales (with α 's of 0.869 and 0.812 for the fear of enacted and self-devaluation subscales, respectively) and good construct validity.

Weight Bias. Weight bias will be examined as encountered or experienced by participants using the Stigmatizing Situations Inventory – Brief (SSI-B; Vartanian, 2015; Appendix E) and personally held biases towards higher weight using the Universal Measure of Bias (UMB-FAT; Latner et al., 2008; Appendix F). The SSI-B is a 10-item scale used to measure experiences of weight stigma, including items such as “Overhearing other people making rude remarks about you in public,” on a Likert scale ranging from 0 (never) to 9 (daily). The SSI-B has demonstrated good internal consistency ($\alpha = 0.91$) and demonstrated good validity with related constructs (Vartanian, 2015).

The UMB-FAT is a 20-item scale that assesses attitudes towards fat, using a 7-point scale with “strongly agree” to “strongly disagree” (Latner et al., 2008). It includes four subscales: negative judgment (dislike towards individuals with overweight or obesity), distance (comfort with individuals with overweight or obesity in social situations), equal rights (assessing the belief that individuals with overweight or obesity deserve legal protection against discrimination) and attraction (the extent to which the participant finds individuals with overweight or obesity to be attractive). The scale has demonstrated adequate internal consistency ($\alpha=.87$), construct validity, and has been demonstrated to directly assess fat bias as opposed to an overall pattern of bias or judgement (Latner et al., 2008).

Healthy Eating. Healthy eating will be assessed through the use of the Dietary History Questionnaire III (DHQ-III; Subar et al., 2001; Appendix G). The DHQ-III was developed using a large, U.S. national nutrient and food group database, and assesses participant caloric intake and macronutrients (including fat, saturated fat, carbohydrates, and protein) and supplies an overall Healthy Eating Index-2015, which is an index assessing compliance with the Dietary Guidelines for Americans (Reedy et al., 2018). The DHQ-III has been found to have reliability for each of the nutrients (Bittoni & Wilkins, 1993).

Physical Activity. Physical activity will be assessed through the revised Morgenstern Physical Activity Questionnaire (PAQ-M; Rubenstein et al., 2011; Appendix H). The PAQ-M measures the frequency of light, moderate, or vigorous physical activity within leisure time. It also assesses physical activity during work, housework, home repairs, yardwork, running errands, caring for others, and includes a question on sedentary activities. The PAQ-M had good

test-retest reliability (intraclass correlation = 0.87) good concurrent validity based on other physical activity questionnaires and BMI.

Eating Behavior. Eating behavior will be assessed using the Three Factor Eating Questionnaire-R18 (TFEQ-18; Angl et al., 2009; Appendix I) to examine overall disordered eating patterns, and the Eating Disorder Diagnostic Scale (EDDS; Stice et al., 2000; Appendix J) will be used for detecting actual eating disorder-related behavior. The TFEQ-18 is an 18-item measure designed to examine eating behavior through cognitive restraint, uncontrolled eating and emotional eating using a 4-point Likert scale, using “definitely true” to “definitely false”. The TFEQ-18 has demonstrated acceptable reliability for each subscale, with alphas of .75 for cognitive restraint, 0.85 for uncontrolled eating, and 0.87 for emotional eating. Further, it has been demonstrated to detect differing eating patterns among a general population (Fleurbaix Laventie Ville Sante (FLVS) Study Group, 2004).

The EDDS – DSM 5 Version is 22-item a questionnaire designed to assess symptoms of anorexia nervosa, bulimia nervosa, and binge-eating disorder per DSM-5 criteria. The questions vary in terms of format, using 6-point Likert ratings from “Not at all” to “Extremely,” dichotomous items and asking about frequency of diagnostically relevant behavior over a set period of time (i.e., days per week for over X amount of months). The EDDS has demonstrated reliability for each disorder, including anorexia (kappa = .95), bulimia (kappa = .71), and binge-eating disorder (kappa = .75). Content validity was established through review by 14 eating disorder experts.

Mental Health. Mental health will be assessed using the 21-item Depression Anxiety and Stress Scale (DASS-21; Appendix K), as it can assess clinically relevant depressive symptoms,

anxious symptoms, and stress all within 21-items (Lovibond & Lovibond, 1995). Participants rate to which extent each symptom applied to them within the past week, from 1 (did not apply to me at all) and 4 (applied to me very much, or most of the time). Each scale has demonstrated good reliability, with α 's = .91, .80, and .84 for Depression, Anxiety, and Stress, respectively (Sinclair et al., 2011). The scale has also demonstrated constructive validity within a large, non-clinical sample (Henry & Crawford, 2005).

In addition, rumination will specifically be examined using the Ruminative Response Scale-Short Form (RRS-SF; Treynor et al., 2003; Appendix L). Wang et al. (2017) found IWB to be moderately and significantly correlated with brooding rumination ($r = .56$) among a sample of individuals with obesity and binge eating disorder. Thus, rumination may be relevant and of interest to aim three as to how IWB may affect weight loss efforts. The RRS-SF includes nine items with two subscales; brooding and reflection. The form utilizes a 4-point Likert scale ranging from 1 ("almost never") to 4 ("almost always") for various aspects of rumination. The two subscales have shown to have acceptable reliability in a clinical and nonclinical samples, with α 's = .79 and .75 for brooding and reflection, respectively. Construct validity was also demonstrated with moderate correlations to the subscales of the DASS-21 (Ruiz et al., 2017).

Self-Esteem. Self-Esteem will be measured utilizing the 10-item Rosenberg Self-Esteem Scale (RSES; Rosenberg, 1965; Appendix M). The RSES uses a 4-point Likert scale from 1 (strongly disagree) to 4 (strongly agree), with higher scores indicating higher self-esteem. The scale has demonstrated good reliability (with an α range of .88 to .90) and convergent validity with other measures of self-esteem (Robins et al., 2001).

Acceptance. Due to the additional third-wave components of treatment, acceptance will also be assessed. The Acceptance and Action Questionnaire – Second Edition (AAQ-II) is a 7-item questionnaire that uses a 7-point Likert scale from 1 (never true) to 7 (always true; Bond et al., 2011; Appendix N). Higher scores indicate less psychological flexibility and higher experiential avoidance. The scale has demonstrated good reliability ($\alpha = .84$) and appropriate convergent validity with measures of psychological distress.

Self-Compassion. In further consideration of the additional third-wave components of treatment, self-compassion will be assessed as well. The Self-Compassion Scale – Short Form (SCS-SF) is a 12-item scale that uses a 5-point Likert scale ranging from 1 (almost never) to 5 (almost always; Raes et al., 2003; Appendix O). The scale has six subscales; the first three represent crucial/core components of self-compassion: self-kindness, common humanity, and mindfulness, and the remaining three serve as counters to these core components, with self-judgement, isolation, and overidentification (becoming wrapped up in negative emotions). The three core components are added together, along with reverse-scored counter components, to create an overall score in which higher scores indicate higher self-compassion. The SCS has good internal consistency ($\alpha = .86$) and good construct validity.

Treatment Acceptability. Upon treatment conclusion, participants will be asked to rate the extent to which they found the treatment to be effective and feasible and the extent to which they felt connected to their behavioral coach using an adapted Satisfaction With Therapy and Therapist Scale—Revised (STTS-R; Po Oei & Green, 2008; Appendix P). The STTS-R assesses satisfaction with therapy and therapist using a 5-point Likert scale, from 1 (Strongly Disagree) to 5 (Strongly Agree). Questions regarding treatment will be adapted for the telehealth, BWLP

situation (i.e., “I am satisfied with the quality of the therapy I received” will be adapted to “I am satisfied with the quality of the telehealth weight loss treatment I received”). Similarly, questions about the therapist will be changed to “weight loss coach.” The STTS-R has been shown to have reliability for both the scale as a whole ($\alpha = .90$) and the subscales Satisfaction with Therapy ($\alpha = .91$) and Client Evaluation of Therapist ($\alpha = .80$).

Statistical Analysis Plan

All analyses will be conducted in SPSS 28 (IBM Corp., 2021). Data will be cleaned and screened before proceeding with analysis. Descriptive statistics will first be examined for the overall sample. Then, demographics among each group will be examined. Preliminary analyses will be run to ensure that there were no significant group differences in terms of basic demographics. Continuous variables will be examined using t-tests or ANOVA (for example, BMI) while dichotomous and categorical variables will be examined using chi-square (i.e., race/ethnicity). While it is hoped that randomization will provide even group characteristics, any potential group differences will be included as a covariate in analyses. Also, upon study conclusion, group differences will also be examined in terms of attrition and number of sessions attended to check whether treatment impacted these factors.

Hypothesis One and Hypothesis Two. A series of 2×2 (time x group) repeated measures ANOVA will be utilized to examine whether the BWLP only and Third-Wave + BWLP groups were successful with lowering weight, IWB, and weight bias and increasing healthy eating and physical activity and whether there are differences between the BWLP only group with the Third-Wave + BWLP group for each outcome.

Exploratory Analyses. Additional 2 x 2 RM-ANOVA's for each outcome variable, including depressive and anxious symptoms, rumination, maladaptive eating, self-esteem, cognitive flexibility and self-judgement will be examined.

Finally, significant changes in weight bias and IWB will be examined as predictors of weight loss and psychological outcomes.

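### The arm comparison tests raw change; adjusting each post score for its own baseline gives more power on the same data (80% to 91% at N=40, if rho is 0.4)

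*Combined protocol and SAP*

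**What the plan says.** The Procedure section states that "participants will be randomly assigned into one of two groups". The Measures section states that "All measures will be completed at baseline and post-intervention online", so each outcome has two time points.

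The sample-size paragraph under Participants says that "a sample size of 40 will be required to detect a medium effect size for a 2 x 2 repeated measures analysis of variance". It then enrols 70 (35 per group) because of attrition concerns. It gives no numeric effect size, alpha, power, pre-post correlation or dropout rate, and does not say which F term was sized.

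Under Hypothesis One and Hypothesis Two, the Statistical Analysis Plan applies a series of 2 x 2 models ("time x group) repeated measures ANOVA will be utilized to examine whether" the groups improved) and asks "whether there are differences between the BWLP only group with the Third-Wave + BWLP group for each outcome". The exploratory outcomes use the same model.

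The only covariate rule is in the opening paragraph of the Statistical Analysis Plan. Preliminary analyses are to show "no significant group differences in terms of basic demographics", with BMI and race/ethnicity as examples, and "any potential group differences will be included as a covariate in analyses". No sentence names an outcome's own baseline score as a routine covariate.

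**The concern.** Both groups receive the DPP, so the between-arm comparison is the only test of the third-wave add-on. With two time points that comparison is a comparison of raw change, which fixes the slope of post on baseline at 1. Unless the pre-post correlation is very high, the true slope is well below 1, and subtracting the whole baseline adds noise.

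Two things are at stake. The first is power, in a trial that expects to lose participants and may finish nearer 40 than 70. The second is chance baseline imbalance. A group that happens to start high tends to fall back, and the raw-change comparison credits part of that fall to its treatment.

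**Working it through.** **Inputs.** From the documents: N=40 required, 70 enrolled, 35 per arm, two time points, randomised. Assumed because not stated: f=0.25 for a medium effect, alpha 0.05 two-sided, equal SDs at both times, and rho shown over a range. D is the arm difference in change in raw-score SDs. In a 2 x 2 interaction with equal arms D = 4f, so f=0.25 means D = 1.0.

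**The plan's 40.** For the within-between interaction, lambda = f² x N x 2/(1-rho), with 1 and N-2 df. At rho 0.4: 0.0625 x 40 x 2/0.6 = 8.33, and power is 80.3%. Forty is the smallest even N reaching 80%. At rho 0.3 or 0.5 the answer would be 46 or 34.

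**Why adjustment gains.** The variance of raw change is 2(1-rho) in units of the outcome variance. The residual variance after baseline adjustment is 1-rho². Their ratio is (1-rho²)/(2(1-rho)) = (1+rho)/2, which is 0.70 at rho 0.4.

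**Power formulas.**
- Planned: lambda = (N/4) x D²/(2(1-rho)), df 1 and N-2.
- Adjusted: lambda = (N/4) x D²/(1-rho²) x (N-4)/(N-3), df 1 and N-3. The last factor allows for estimating the baseline slope.

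At N=40, D=1.0, rho 0.4, the adjusted lambda is 10/0.84 x 36/37 = 11.58, and power is 91.2%. At N=30 it is 7.5/0.84 x 26/27 = 8.60, which still gives just over 80%.

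| rho | Power at N=40, D=1.0 (planned / adjusted) | Total N for 80%, D=1.0 | Detectable D at 80%, 70 completers |
|---|---|---|---|
| 0.3 | 74% / 89% | 46 / 32 | 0.80 / 0.65 |
| 0.4 | 80% / 91% | 40 / 30 | 0.74 / 0.63 |
| 0.5 | 87% / 94% | 34 / 28 | 0.68 / 0.59 |
| 0.7 | 98% / 99% | 22 / 20 | 0.53 / 0.49 |
| 0.9 | – | – | 0.30 / 0.30 |

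Simulation with 40,000 trials at N=40 and rho 0.4 gave 80.6% against 91.2%. Both methods estimated a mean difference of 1.00 SD. Under the null they rejected 4.9% and 5.0% of the time.

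**Equivalent sample size.** Seventy adjusted completers do the work of 70/((1+rho)/2): 100 at rho 0.4, 93 at 0.5, 82 at 0.7. The only retest figure in the documents is for the PAQ-M, "test-retest reliability (intraclass correlation = 0.87". If that were the pre-post correlation, 70 would do the work of 75.

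**Chance imbalance.** With 35 per arm, the baseline difference has SD √(2/35) = 0.239 outcome SDs. The raw-change estimate moves the opposite way by (1-rho) of whatever difference occurs. An imbalance of 0.48 SD is 0.48/0.239 = 2.0 standard errors, reached or exceeded in about 1 outcome in 20. At rho 0.5 it shifts the estimate by 0.5 x 0.48 = 0.24 SD. In null simulations at N=70, restricted to imbalances of 0.45 to 0.51 SD, the planned test rejected 15% (rho 0.4), 13% (0.5) and 11% (0.7) of the time. The adjusted test stayed at about 5%. Over all trials, both hold 5%.

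**WBIS.** Entry requires a score of 4 or higher, which narrows the baseline spread. If the cutoff is near the population mean and the screening score serves as baseline (both assumed), the variance falls by 6% to 16% for unselected rho 0.7 to 0.3, rather than 15% to 35%.

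**The case against.** The planned test is valid and conventional. It has the correct overall type I error, estimates the same quantity, and answers the time and group questions in one model. That stands: this is lost efficiency, not an error.

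The 80% to 91% figure depends on a rho chosen because it returns 40, and on the attrition floor. If all 70 complete, the gain at D=1.0 and rho 0.4 is 96.4% to 99.4%, only 3 points. That is correct, but f=0.25 here means a full 1.0 SD arm difference. At 0.5 SD and rho 0.4, power is 47% against 61% with 70 completers and 29% against 38% with 40. The gain is therefore material with full retention, though adjustment does not make the trial well powered for a difference of that size.

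The gain is smaller for the WBIS, a direct measure of what the add-on targets. Under the truncation assumptions above, the N=40, D=1.0, rho 0.4 case gives 87.8% against 91.2%. This stands, and it limits the benefit there. The same holds for any outcome with high rho, and body weight is probably one.

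The covariate rule might be read to cover outcome baselines, since BMI is one of its examples. A 5% test flags about 53% of imbalances of 0.45 to 0.51 SD at N=70, and the null rejection rate in those trials would then be about 8% to 9% rather than 13% to 15%. The text speaks of basic demographics, so this is the less literal reading. Even so, adjustment would depend on an observed difference, and the power gain would be lost whenever none was flagged.

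**Conclusion.** The concern holds. Routine adjustment for each outcome's own baseline is not planned, and it would give a more precise estimate of the same arm difference from data already being collected. The size depends on the unstated rho: an 11-point power gain at N=40 and D=1.0 if rho is 0.4, 7 points at 0.5, and about 1 point at 0.7. The calculations assume alpha 0.05, equal SDs and a roughly linear relation between baseline and post scores. The required 40 is reproducible and is not disputed. This should be fixed because the improvement is free, not because the planned test is invalid.

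**What to change.** For the arm comparison in each outcome, specify in the Statistical Analysis Plan a linear model of the post-intervention score on arm and that outcome's baseline score, run in SPSS. Fix it in advance, so that it does not depend on any preliminary test of group differences. Report the adjusted arm difference with its 95% confidence interval. Keep the time term of the repeated measures ANOVA for the question of change over time.

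The cost is one model per outcome and one residual degree of freedom. Participants, visits, measures and software are unchanged. The linearity assumption should be checked.

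### Is the sample size of 40 for a medium effect wrong because the plan does not say which ANOVA term was powered?

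*Combined protocol and SAP*

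**What the plan says.** The sample-size paragraph in the Participants section reports a G*Power result: "a sample size of 40 will be required to detect a medium effect size for a 2 x 2 repeated measures analysis of variance". It defends the choice of a medium effect partly by precedent and partly because "this study aims to examine the efficacy of an intervention", for which a small effect would be of less clinical value. Allowing for attrition, "the sample size for the proposed study will be 70, with 35 individuals per group". It gives no numerical effect, effect metric, alpha, power, correlation between the two measurements, outcome or attrition rate.

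The Interventions section gives the weight loss program to everyone. The Procedure section adds that "only one group will be administered a third-wave, ACT and self-compassion-based IWB intervention for 30 minutes". Under Hypothesis One and Hypothesis Two, the Statistical Analysis Plan uses one 2 × 2 repeated measures ANOVA per outcome for two questions: whether participants improved over time, and whether the arms differ.

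**The concern.** Because both arms receive the weight loss program, the pooled time effect says nothing about what the added module contributes. Within the planned ANOVA, the time by group term answers that question. A reader who sees a medium effect tied to intervention efficacy may assume that 40 completers are enough to show a medium benefit of the module.

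That need not follow. In a 2 × 2 design, the same f describes a much larger arm difference when applied to the interaction than the mean change it describes when applied to time. If 40 was chosen with the time effect in mind, or with f = 0.25 entered without translating it, the trial might have little chance of detecting an arm difference of half an outcome SD. A non-significant interaction could then be misread as ruling out a medium benefit.

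**Working it through.** **Inputs from the documents.** 40 required and 70 enrolled, 35 per arm (Participants); two measurements, baseline and post-intervention (Measures); 2 × 2 repeated measures ANOVA (Statistical Analysis Plan).

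**Assumed, because not stated.** Two-sided alpha 0.05; f = 0.25 for a medium effect; equal arms; independent participants; baseline-to-post correlation ρ shown over a range. Figures in outcome SD also assume equal SDs at both visits.

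**1. Can 40 be reproduced?** Under G*Power's default option, the noncentrality for time and for time by group is the same:

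λ = N·m·f²/(1 − ρ), with m = 2 and df 1 and N − 2.

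At N = 40 this is 40 × 2 × 0.0625/(1 − ρ) = 5/(1 − ρ).

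| ρ | λ | Power at 40 |
|---|---|---|
| 0.40 | 8.33 | 80.3% |
| 0.50 | 10.00 | 86.9% |
| 0.55 | 11.11 | 90.1% |

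At 80% power, the smallest even N is exactly 40 at ρ = 0.4 and 34 at ρ = 0.5. Two other readings do not give 40. At 80% power the between-group main effect needs 98 (at ρ = 0.5), and the variant with λ = N·f² needs 128. So 40 cannot be traced to a single set of inputs, but it fits an ordinary calculation for either term of interest.

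**2. What does f = 0.25 mean for each term?** It corresponds to cell effects of ±0.25 SD.
- Time: both arms move from −0.25 to +0.25, a change of 0.5 SD.
- Time by group: one arm changes by +0.5 and the other by −0.5 around the common trend, so the difference in change is 4 × 0.25 = 1.0 SD.

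Check: at ρ = 0.5 the change-score SD is √(2 × 0.5) = 1 outcome SD. A difference of 1.0 with 20 per arm then has t noncentrality 1.0 × √(20/2) = 3.162, whose square is 10. That is the λ in the table.

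**3. What arm difference can be detected?** In a 2 × 2 design the interaction test is a two-sample t test on change scores. Solving the noncentral t for 80% power gives d = 0.909 change-score SD at 20 per arm and 0.679 at 35 per arm. In outcome SD, D = d·√(2(1 − ρ)). The two outer columns on the right show power for an illustrative D = 0.5.

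| ρ | Detectable D, 40 completers | Detectable D, 70 completers | Power for D = 0.5, 40 | Power for D = 0.5, 70 |
|---|---|---|---|---|
| 0.5 | 0.91 | 0.68 | 34% | 54% |
| 0.7 | 0.70 | 0.53 | 51% | 76% |
| 0.8 | 0.57 | 0.43 | 68% | 90% |
| 0.85 | 0.50 | 0.37 | 80% | 96% |
| 0.9 | 0.41 | 0.30 | 93% | 99.6% |

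The correlation needed for 80% power at D = 0.5 is ρ = 1 − (0.5/d)²/2. This gives 1 − (0.5/0.909)²/2 = 0.849 at 40 completers and 1 − (0.5/0.679)²/2 = 0.729 at 70.

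**4. What does enrolling 70 add?** Falling from 70 to 40 would be a loss of 1 − 40/70 = 42.9%, so the plan reaches its stated requirement unless attrition exceeds that. If all 70 complete, power at f = 0.25 is 98.5% at ρ = 0.5 and still 83.0% at ρ = 0.

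**The case for a change.** The strongest case for a change runs as follows. The plan justifies its effect size by the efficacy of an intervention, and the only intervention that differs between arms is the module. On the usual two-group scale, a medium effect is half an SD. With 40 completers and ρ = 0.7, power for that is 51%, so a real benefit of this size would be missed about half the time. The detectable differences of 0.91 and 0.68 change-score SD depend on neither the 0.5 yardstick nor ρ. A single effect label also cannot describe weight, diet and questionnaire outcomes, whose correlations will differ.

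Much of this stands. The omission is real, the arithmetic is right, and the between-arm meaning of f = 0.25 is larger than the word medium suggests. The test-retest value of 0.87 given for the physical activity questionnaire does not rescue the argument for that outcome, since it is not a baseline-to-post correlation under treatment.

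What does not stand is the step from there to a defect. The plan says medium for a repeated measures ANOVA run in G*Power, where f is the natural scale. The 0.5 outcome-SD arm difference comes from outside the plan. Even if time by group was the powered term, f = 0.25 gives 40. No figure in the plan is shown to be missed.

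**Conclusion.** The concern does not hold as a fault in the sample size. The Participants section leaves out the inputs to its calculation, but 40 is a legitimate result for either ANOVA term, with 80% to 90% power at f = 0.25 and ρ from 0.4 to 0.55. Supplying the missing inputs would leave enrolment, the planned ANOVA and its results as they are. A statistician interpreting the arm comparison can work out what it could detect from the design alone: at 80% power, 0.91 change-score SD with 40 completers, or 0.68 with 70 completers and no dropout. Such a reader would not take a non-significant interaction as excluding a half-SD benefit.

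These figures rest on two-sided alpha 0.05, equal arms and independent participants. Participants "attend weekly online groups", so independence is an approximation, and the documents give no intraclass correlation from which to refine it. The outcome-SD figures also need equal SDs at both visits. That is doubtful for the WBIS, which is screened at baseline "with a cutoff of 4 or higher"; the documents give no SDs from which to quantify the effect. The figures for a 0.5 outcome-SD arm difference are an illustration, not a target that the plan set and missed.
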